H.5.1. *Prehospital Phase Randomization:* Individual patients meeting criteria while en route via emergency medical transport will be randomized using an allocation sequence block size of 8 to either 1 gram of tranexamic acid or placebo diluted in 100cc of normal saline given over approximately 10 minutes. A single prehospital treatment box containing ascending numerically labeled (1-8) treatment packs (randomized with a computer random number generator) will be distributed to each respective helicopter base (or station in the case of ground ambulance). In an ascending numerical order fashion treatment packs will be utilized for enrolled patients. The box and treatment pack # will be recorded by research staff upon arrival for all randomized patients. The patient and all treatment and research staff will be blinded to the treatment arm. All intervention vials will be covered to obscure view of vial contents to prehospital staff giving the intervention and amber colored syringes will be utilized to maintain blinding. IDS at the University of Pittsburgh will be unblinded to the prehospital intervention. Additionally, the pharmacy at each respective participating center will have access to the prehospital randomization/assignment scheme once the prehospital intervention box and treatment # are provided to them by the accepting research staff at each participating center.

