J.1.1. Primary Primary Outcome (30 Day Mortality): All randomized subjects will be included in the analysis to test the differences in 30 day mortality. 30 day mortality will be computed at the end of study and stated as a dichotomous variable. For subjects who have not been reported as deceased by day 30 following admission from any of the sources queried we will use multiple imputation under the assumption that the missing data are not missing at random. The process for determining whether or not a subject is deceased at 30 days is described in detail in section (N.6.). If more than 15% of the subjects are missing the 30 day outcome, we will consider this outcome as descriptive only. We will analyze this endpoint as a fixed point in time using a two-sided Mantel-Haenszel (M-H) test taking site, the stratifying variable (strata), into account. The M-H test is robust to lack of homogeneity of odds ratio although power would be reduced. This approach has more power than the survival analysis described below given the potential for crossing hazard functions. We will also test homogeneity of the odds ratios across sites using the Breslow-Day test. We will compute 95% confidence intervals on mortality by treatment group at 30 days. We will also conduct a sensitivity analysis of 30 day mortality to assess the effect of imputation 'as alive' on the treatment group comparisons and confidence limits for the 30 day outcome. To provide further insight we will compute 30-day survival curves. Survival time will be compared between treatment arms using Cox proportional hazards model with site as a covariate. If the proportional hazards assumption is violated we will include a time treatment interaction in the model and choose the appropriate approach. As an additional analysis, we will use the same Cox proportional hazards approach to adjust for baseline covariates such as demographics, injury severity, presenting vital signs, and prehospital time. Since site is a stratifying variable it will be included as a random effect. We will do pre-screening of covariates other than site at the 0.20 level before fitting the final model if our sample size is not sufficient to include all covariates in the model. We would follow the approach above to test for and take crossing hazards into account if applicable. As an additional exploratory analysis we will compare 30-day survival in the two groups adjusting for the covariates listed above and any additional baseline covariates that are imbalanced between treatment groups ($p < 0.10$) using the same screening approach to decrease the number of covariates included in the model, if necessary.

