
J.2. Analysis of Prehospital Randomized Secondary Outcomes: Unless there is sufficient power (predetermined before the analysis is begun), the approach to analysis of secondary endpoints will generally be calculation of confidence limits on intervention group differences or model parameters rather than formal tests of significance at a specified critical level as the trial will not have sufficient power to detect difference in all of these outcomes. However, these comparisons will add to the knowledge of the benefits and risks of the interventions. Parametric and nonparametric comparisons will be applied according to normalcy. All tests used will be two-tailed tests at significance level (α) of 0.05. For prehospital randomized clinical outcomes we will use Chi-square with 95% confidence intervals for dichotomous outcomes and parametric or non-parametric testing for continuous variable with 95% confidence intervals. For prehospital randomized laboratory or exploratory outcomes we will use parametric or non-parametric testing for continuous variable with 95% confidence intervals.

J.3. Analysis for Second Stage In-hospital Randomized Dosage Regimens: Chi-square test will be able to test the effect of different tranexamic dosage regimens on hyperfibrinolysis. Similarly, chi-square will be used to detect any differences between dosage groups for 30 day mortality. To detect a trend in dosage response, test for trend will be implemented. As additional analysis and to account for site and to adjust for some important covariates, we will use logistic regression to test the effect of dosage on hyperfibrinolysis. Similarly Cox proportional hazards regression can be used for 30 day mortality. *For In-hospital randomized dosage regimen comparison for clinical outcomes* we will use Chi-square with 95% confidence intervals for dichotomous outcomes and parametric or non-parametric testing for continuous variable with 95% confidence intervals. *For In-hospital randomized dosage regimen comparison for laboratory or exploratory outcomes* we will use parametric or non-parametric testing for continuous variable with 95% confidence intervals.

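### J.2 omits site from the secondary comparisons although site is the declared stratifying variable, so intervals on differences are as wide as or wider than the design supports, probably by little

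*Combined protocol and SAP*

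**What the plan says.** **Primary outcome.** J.1.1 analyses 30-day mortality with a "two-sided Mantel-Haenszel (M-H) test taking site, the stratifying variable (strata), into account". It also tests homogeneity of the odds ratio across sites and carries site in the supporting Cox models; for the covariate-adjusted one it says "Since site is a stratifying variable it will be included as a random effect".

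**Randomisation.** Under H.5.1 patients are "randomized using an allocation sequence block size of 8". Each box of eight packs is held at one helicopter base or ground station and used in numerical order. Complete boxes are thus balanced within base, and a site's total is balanced apart from part-used boxes.

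**Secondary outcomes of the prehospital randomisation.** J.2 prefers "calculation of confidence limits on intervention group differences or model parameters rather than formal tests of significance", unless power is judged sufficient in advance. Where tests are made, "All tests used will be two-tailed tests at significance level" 0.05. For clinical outcomes it specifies "we will use Chi-square with 95% confidence intervals for dichotomous outcomes" and "parametric or non-parametric testing for continuous variable with 95% confidence intervals"; the laboratory outcomes get the same continuous methods. Site does not appear in J.2.

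**In-hospital dose comparison.** J.3 also leads with chi-square, but it adds a logistic regression that accounts for site, as an additional analysis, for dose and hyperfibrinolysis.

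**The concern.** When allocation is balanced within a factor that predicts outcome, differences between levels of that factor cancel out of the treatment comparison. An analysis that ignores the factor still counts those differences as noise. Its standard error for a treatment difference is then too large, and the interval covers more often than 95%.

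This matters in J.2 because the confidence limits are the main result there, and the section itself says that the trial lacks power for all of these outcomes. There is also an unexplained inconsistency: death at 30 days is compared within site, while death at 24 hours is pooled over sites.

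**Working it through.** **1. The plan's own figure.** The documents state no interval width or power for any secondary outcome. The nearest figure is the K.1 table: 497 per arm, control rate 16%, two-sided alpha 0.05, pooled variance. Recomputing gives power 0.9001, 0.8505 and 0.7996 at treatment rates 0.0919, 0.0965 and 0.1003, against the stated 0.90, 0.85 and 0.80. The table reproduces, so 497 per arm and the pooled-variance form are used below.

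**2. Inputs.** From the documents: 497 per arm (K.1) and four sites (DSMB charter). Assumed: equal site sizes, exact 1:1 balance within site, and all site rates and intraclass correlations (ICC), because the documents give none.

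**3. Formulas for a risk difference, no treatment effect.** With site rates p_s and overall rate P:

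- Unstratified variance = P(1−P) × 2/497
- Site-stratified variance = mean of p_s(1−p_s) × 2/497
- Mean of p_s(1−p_s) = P(1−P) − V, where V is the between-site variance of the rates
- Width ratio, stratified to unstratified = sqrt(1 − V / [P(1−P)]), which cannot exceed 1

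**4. Worked example.** Sites at 8, 13.3, 18.7 and 24%, so P = 0.16 and P(1−P) = 0.1344.

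- V = (0.08² + 0.027²)/2 = 0.00356
- Unstratified half-width = 1.96 × sqrt(0.1344 × 2/497) = 0.0456
- Stratified half-width = 1.96 × sqrt(0.1308 × 2/497) = 0.0450
- Ratio 0.987, so the unstratified interval is about 1.4% too wide

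**5. Range.** Rates are evenly spaced between the limits shown. Coverage of the unstratified interval comes from 20,000 simulated trials with 124 patients per arm per site and no treatment effect. The Monte Carlo standard error is sqrt(0.05 × 0.95 / 20,000) = 0.0015.

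| Overall rate | Site rates (assumed) | Half-width unstratified | Half-width stratified | Ratio | Excess width | Coverage |
|---|---|---|---|---|---|---|
| 5% | 2.5-7.5% | 0.0271 | 0.0270 | 0.996 | 0.4% | not simulated |
| 16% | all 16% | 0.0456 | 0.0456 | 1.000 | 0% | 0.948 |
| 16% | 12-20% | 0.0456 | 0.0454 | 0.997 | 0.3% | 0.949 |
| 16% | 8-24% | 0.0456 | 0.0450 | 0.987 | 1.4% | 0.951 |
| 16% | 4-28% | 0.0456 | 0.0442 | 0.970 | 3.1% | 0.956 |
| 30% | 15-45% | 0.0570 | 0.0553 | 0.970 | 3.1% | 0.954 |
| 30% | 10-50% | 0.0570 | 0.0539 | 0.946 | 5.8% | 0.962 |
| 50% | 25-75% | 0.0622 | 0.0577 | 0.928 | 7.8% | 0.965 |

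When sites are identical, the simulated stratified interval is 0.1% wider (ratio 1.0010), a finite-sample term that can be ignored.

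**6. Tests.** In the 25-75% case, chi-square rejects a true null in 0.035 of trials, against 0.048 for Mantel-Haenszel. With a 6-point effect, stratifying raises power from 0.814 to 0.823 (sites 8-24%) and from 0.573 to 0.600 (sites 15-45%).

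**7. Continuous outcomes.** The width ratio is sqrt(1 − ICC): 0.995 at ICC 0.01, 0.975 at 0.05 and 0.949 at 0.10.

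**8. Odds ratios.** The direction reverses. With sites at 8-24% and no effect, the standard error of the log odds ratio is 0.1739 crude and 0.1763 Mantel-Haenszel, although the stratified test has the greater power.

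**The case against.** **Size.** The strongest objection is that this hardly matters. Section R speaks only of potential variation in care and says that similar level 1 centres were chosen to limit it; H.8 adds common procedures for resuscitation and transfusion. With sites at 12-20% or 8-24%, the unstratified interval has nominal coverage to within simulation error. This stands, and it limits the point to a small gain in precision.

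**Validity.** A reader might infer that the J.2 intervals are definitely too wide, or that the secondary inferences are invalid. The documents support neither. The excess is zero if sites are alike, and any error is conservative: it adds no bias and does not inflate type I error.

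**J.3.** A reader might extend the point to the dose comparison. That does not follow. J.3 already names a site-adjusted logistic regression for hyperfibrinolysis, if only as an additional analysis. H.5.2 gives a block size of 9 for the in-hospital sequence but does not say that the sequence is stratified by site, so the balance that drives the argument is not documented there.

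**Other planned analyses.** I.4.2 to I.4.4 name multivariate Cox regression for lung injury, nosocomial infection and organ failure, and J.2 allows limits on model parameters. So unadjusted comparisons are not the only ones planned. Neither place says that site is in the model, so the gap remains.

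**Level of blocking.** The blocks sit at base or station, which is finer than site. Adjusting for site recovers only part of what the blocking offers. That is a limit of the fix, not an argument against it.

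**Conclusion.** The point holds in a limited form. J.2 leaves out the factor that J.1.1 calls the stratifying variable and that the prehospital allocation approximately balances. On the difference scale the resulting 95% intervals are as wide as or wider than the design supports.

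The excess is 0% if sites do not differ, about 0.3% to 3% for moderate spreads and about 6% to 8% only for extreme ones, such as a five-fold range of 10-50%. These sizes rest on four equal sites, exact balance within site and assumed site rates, so they show a range and do not estimate what the trial will see. The conclusion covers differences in proportions and means under the prehospital randomisation. It does not cover odds ratios or J.3. This is an inexpensive improvement, not a flaw that threatens any conclusion.

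**What to change.** In J.2:

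- **Binary secondary outcomes:** replace the chi-square test with the site-stratified Mantel-Haenszel test, and report the Mantel-Haenszel risk difference stratified by site with its 95% interval. Name the variance estimator.
- **Continuous secondary outcomes:** use a linear model with site as a covariate or, where a rank method is preferred, the site-stratified (van Elteren) test. The rank test yields no interval by itself, so state which estimate and interval will accompany it.
- **Cox models in I.4.2 to I.4.4:** say whether site is included.

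J.3 need not change on this ground. The cost is analysis-plan wording, ideally settled before unblinding. Site is already recorded and the Mantel-Haenszel method is already in the plan. If sites turn out alike, the loss of precision on differences is negligible.

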Secondary Hypothesis 3B: Prehospital tranexamic acid as compared to placebo will attenuate trauma-induced pro-inflammatory changes and immunosuppression by reducing the early inflammatory cytokine response (GM-CSF, IFN- γ , IL-1 β , IL-2, IL-4, IL-5, IL-6, IL-8, IL-10 and TNF- α), HMGB1 levels and early inflammatory gene responses as measured by RT-PCR.

E.3.4. Secondary Aim#4: Determine whether different dosing regimens of tranexamic acid upon arrival in the hospital are associated with improvements in hyperfibrinolysis, markers of coagulopathy, clinical outcomes, platelet and leukocyte activation and the early inflammatory response.

Secondary Hypothesis 4A: Repeat dosing of 1 gram of tranexamic acid followed by 1 gram over approximately 8 hours after hospital arrival in patients who have already received 1 gram of prehospital tranexamic acid will lower the incidence of 12 hour (from arrival) hyperfibrinolysis (estimated percent lysis > 7.5%), coagulopathy (INR > 1.4) and improve r-TEG markers of coagulopathy, D-dimer levels, activated protein C levels and plasmin-antiplasmin complex levels as compared to standard dosing of tranexamic acid (1 gram over approximately 8 hours) or abbreviated dosing (no additional tranexamic acid).

Secondary Hypothesis 4B: Repeat dosing of 1 gram of tranexamic acid followed by 1 gram over approximately 8 hours after hospital arrival in patients who already received prehospital tranexamic acid will lower the incidence of 24 hour and 30 day mortality, acute lung injury, multiple organ failure and nosocomial infection as compared to standard dosing or abbreviated dosing.

Secondary Hypothesis 4C: Repeat dosing of 1 gram of tranexamic acid followed by 1 gram over approximately 8 hours after hospital arrival in patients who already received prehospital tranexamic acid will reduce 12 hour (from arrival) base deficit, 24 hour crystalloid requirements and 6 hour and 24 hour blood and blood component transfusion requirements (PRBC, FFP and platelets) as compared to standard dosing or abbreviated dosing.

Secondary Hypothesis 4D: Repeat dosing of 1 gram of tranexamic acid followed by 1 gram over approximately 8 hours after hospital arrival in patients who already received prehospital tranexamic acid will reduce 12 hour and 24 hour (from arrival) markers for platelet and leukocyte activation, plasmin

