H.3.1. Prehospital Phase Intervention: Once inclusion and exclusion are verified while the patient is being transported via emergency medical transport to a STAAMP trial participating center, in a randomized, double blinded fashion, either 1 gram bolus of tranexamic acid diluted in 100cc of normal saline (pre-prepared on emergency vehicle) or placebo of identical volume will be infused intravenously or intraosseously (if IO access was obtained due to a clinical need per standard of care) into the patient over approximately 10 minutes (“Bag A”). After receiving the prehospital phase intervention, standard operating procedures utilizing goal directed crystalloid infusion will be followed (see **H.7. Prehospital Standard Operating Procedures** below)

H.3.2. In-hospital Phase Intervention: Upon arrival, patient blood and labs will be sampled and arrival rapid-TEG analysis will be performed within first 6 hours. After inclusion and exclusion criteria verification by research staff, in a double blinded, randomized fashion, those patients who received tranexamic acid in the prehospital phase will receive 1 of 3 different dosage regimens:

1. Standard Tranexamic acid Dosing: 1 gram infusion over approximately 8 hours
2. Repeat Tranexamic acid Dosing: 1 gram bolus **and** 1 gram infusion over approximately 8 hours
3. Abbreviated Tranexamic acid Dosing: No further tranexamic acid to be given

For intervention blinding purposes, each patient will receive both a bolus dose (either tranexamic acid or placebo), “Bag B,” and 8 hour infusion (either tranexamic acid or placebo), “Bag C,” depending on the randomized dosing regimen. (Figure 13. below)

H.3.2.1 Adjustment For Renal Insufficiency: Subjects with a known or suspected history of renal insufficiency will receive a renal dose adjustment for the 8 hour repeat infusion (Bag C). The Estimated Body Weight Table will be used to determine the dose (Figure 12). The dose will be capped at 1000 mg.

1. Standard Dosing: bolus- no dose adjustment / infusion- 1.25 mg/kg/hr x 8hrs
2. Repeat Dosing: bolus- no dose adjustment / infusion- 1.25 mg/kg/hr x 8hrs
3. Abbreviated Dosing: bolus- no dose adjustment / infusion- 1.25 mg/kg/hr x 8hrs

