I.2 Secondary Clinical Outcomes: Secondary clinical outcomes will include the incidence of hyperfibrinolysis (EPL > 7.5% by rapid-TEG analysis) upon arrival to the trauma bay within the first 6 hours, the incidence of acute traumatic coagulopathy (INR > 1.4), 24 hour mortality, acute lung injury, multiple organ failure, the development of nosocomial infection, early (24hr) seizures, in-hospital pulmonary embolism, presenting base deficit, 24 hour crystalloid requirements and 6 hour and 24 hour blood and blood component transfusion requirements (PRBC, FFP and platelets). *These same clinical outcomes will similarly be used for the randomized tranexamic acid dosage regimen comparison.*

I.3. Secondary Laboratory/Mechanistic Outcomes: All laboratory/mechanistic outcomes will be measured during the first 6 hours from trauma center arrival and at 12 and 24 hours (+/- 12 hours) out from injury. Those laboratory/mechanistic outcomes including flow cytometry which require fresh blood samples will be performed only at the University of Pittsburgh on a subset of patient samples unless participating centers have specific capabilities and following appropriate training for standardization. *These same laboratory/mechanistic outcomes will similarly be used for the randomized tranexamic acid dosage regimen comparison at 12 and 24 hours post-injury.*

I.4. Clinical Outcomes Methods/Definitions: All clinical outcomes will be prospectively evaluated for throughout ICU and hospital admission and the timing from the day of initial injury will be recorded for time-to-event statistical analysis.

I.4.1. 30 day and 24 hour mortality: 30 day mortality will be prospectively recorded from the day of trauma bay arrival. Over the first 24 hours we will document and record the time of death in hours. We suspect that patients enrolled will have a significant percentage of mortality that occurs in the first 24hrs.

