I.5. Laboratory/Mechanistic Outcome Methods/Definitions: All measurements will be performed within 6 hours of arrival and at 12 and 24 hours post injury (+/- 12 hours) for the randomized dosage regimen comparison. One more additional blood sample will be collected at 72 hours (\pm 12 hrs) for D-dimer, activated Protein C levels and plasmin-antiplasmin complexes measurements. Excluding r-TEG analysis and PT/ INR measurements, all blood and serum samples will be spun, stored and batched at their respective institution and delivered to the University of Pittsburgh where formal ELISA immunoassay measurements will be undertaken. Those laboratory/mechanistic outcomes including flow cytometry which require fresh blood samples will be performed only at the University of Pittsburgh on a subset of patient samples unless participating centers have specific capabilities and following appropriate training for standardization.

I.5.1. Coagulopathy and TEG parameters (Aim#2): To appropriately characterize differences in coagulopathy between tranexamic acid and placebo, in addition to r-TEG measurements of hyperfibrinolysis, presenting PT/ INR and additional TEG parameters will also be measured (ACT, r-value, k-time, α -angle, maximal amplitude, and G-values). All rapid TEG measurements will be performed within 6 hours of arrival and at 12 and 24 (+/- 12 hours) hours post injury. TEG analysis will be performed on a TEG[®] 5000 Thromboelastograph[®] Hemostasis Analyzer which will reside within the emergency department of each participating site. Standard laboratory INR will be drawn and measured at each institution within 6 hours of arrival and at 12 and 24 hours (+/- 12 hours). To further quantify the coagulopathy and hyperfibrinolysis post injury in these patients, D-dimer, activated Protein C levels and plasmin-antiplasmin complexes will be measured by ELISA plate assay. (ANIARA, USCN Life Science Inc., DRG International, Inc.) Plasmin-antiplasmin complexes may represent a more common, subclinical measurement of fibrinolytic activity that is not able to be assessed using standard TEG analysis, but elevated levels are associated with significantly worse outcome post injury and may be a marker than demonstrates the mechanism by which tranexamic acids has it beneficial effects.

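### Optional gain in precision: adjust the regimen comparison of continuous 12- and 24-hour markers and 12-hour base deficit for an arrival value drawn before Bag B

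*Combined protocol and SAP*

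**What the plan says.** Section J.3 covers the second-stage comparison of the standard, repeat and abbreviated regimens. For continuous laboratory and exploratory outcomes it states: "we will use parametric or non-parametric testing for continuous variable with 95% confidence intervals". Continuous clinical outcomes are handled in the same way. No arrival value, change from arrival or repeated-measures model is named.

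Adjusted models appear in J.3 only as additional analyses of two other outcomes. One is "to adjust for some important covariates, we will use logistic regression to test the effect of dosage on hyperfibrinolysis", with the covariates left unnamed. The other is "Similarly Cox proportional hazards regression can be used for 30 day mortality".

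The earlier measurements exist. Section I.3 says: "All laboratory/mechanistic outcomes will be measured during the first 6 hours from trauma center arrival and at 12 and 24 hours". Section I.5 gives the same schedule. Presenting base deficit is a secondary outcome in I.2, and Hypothesis 4C in E.3.4 says repeat dosing "will reduce 12 hour (from arrival) base deficit". Section H.3.2 describes arrival sampling ahead of the regimens: "Upon arrival, patient blood and labs will be sampled and arrival rapid-TEG analysis will be performed within first 6 hours".

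**The concern.** Every patient in this comparison has already had prehospital tranexamic acid. A value drawn on arrival before Bag B is therefore a true baseline for the second randomisation. H.2 deliberately recruits across a range of injury severity, so markers are likely to vary widely between patients. An unadjusted comparison leaves in the error term whatever part of that variation the arrival value could explain.

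What is at stake is the width of the intervals for Aim 4. The sample size in section K rests on 30-day mortality alone, and no power is given for the regimen comparison. J.2 concedes, for the prehospital secondary outcomes, that power will be lacking for some and that confidence limits will generally be reported instead. The regimen groups are about a third the size of a prehospital arm, so precision matters more there.

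**Working it through.** **Inputs from the protocol.** 497 patients per prehospital arm (K.1); three regimens in blocks of 9 (H.5.2), from which equal allocation is inferred; two-sided alpha 0.05 (stated in J.2, assumed to apply to J.3).

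**Assumed inputs.** Neither of these is in the documents:
- rho, the correlation of the arrival value with the later value: 0.3 to 0.7, with 0.2 as a low case.
- f, the share of patients with a value drawn before Bag B: 1 or 0.5.

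**Check of the plan's own figure.** For 9.65% against 16%, pooled-variance z-test, 85% power, the mean proportion is 0.12825:

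n = [1.96 × √(2 × 0.12825 × 0.87175) + 1.036 × √(0.0965 × 0.9035 + 0.16 × 0.84)]² / 0.0635² = 496.3, so 497 per arm.

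This agrees with K.1. The plan has no corresponding figure for continuous markers.

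**Patients per regimen.** 497 / 3 = 165.7, about 166. This is a ceiling. Deaths before 12 or 24 hours, opt-outs and missing samples reduce it, and flow cytometry is done only on a subset, mainly at one site.

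**Variance factor.** With covariance adjustment, patients with a usable arrival value contribute residual variance 1 - rho². Those set to the mean with an indicator contribute 1. The average is f(1 - rho²) + (1 - f) = 1 - f × rho², provided missingness is unrelated to outcome. Interval width scales with the square root of this factor, and the equivalent number per regimen is 166 divided by it.

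**Detectable difference.** Unadjusted, for one pair of regimens at 80% power: (1.960 + 0.842) × √(2/166) = 0.308 SD. Adjusted, this is multiplied by the square root of the variance factor.

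| rho | f | Variance factor | Interval width factor | Equivalent n per regimen | Detectable difference (SD) |
|---|---|---|---|---|---|
| 0.3 | 1 | 0.910 | 0.954 | 182 | 0.293 |
| 0.5 | 1 | 0.750 | 0.866 | 221 | 0.266 |
| 0.7 | 1 | 0.510 | 0.714 | 325 | 0.220 |
| 0.3 | 0.5 | 0.955 | 0.977 | 174 | 0.301 |
| 0.5 | 0.5 | 0.875 | 0.935 | 190 | 0.288 |
| 0.7 | 0.5 | 0.755 | 0.869 | 220 | 0.267 |

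At rho 0.2 the variance falls by 4% with f = 1 and by 2% with f = 0.5.

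**Simulation for f = 1.** In 4,000 runs per rho, with 166 per group and a true difference of 0.30 SD, the variance ratios (adjusted to unadjusted) at rho 0.3, 0.5 and 0.7 were 0.91, 0.78 and 0.50. The formula gives 0.91, 0.75 and 0.51. Power rose from about 0.78 without adjustment to 0.82, 0.89 and 0.97.

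**The case against.** The strongest objection is to the baseline itself. A reader might infer from H.3.2 that the arrival sample always precedes the in-hospital regimen. The text gives only that order of description: the condition for giving a regimen is verification of eligibility, not completion of sampling. The arrival window runs to 6 hours, and nothing requires the draw before Bag B. A sample taken after Bag B has started may already carry part of the regimen effect, and adjusting for it would remove that part. This stands. Only pre-Bag B values can be used, and the gain depends on f as well as rho.

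The meaning of rho is also unsettled. I.3 and I.5 count the 12- and 24-hour samples from injury with a 12-hour tolerance; Hypotheses 4A, 4C and 4D count from arrival. If the tolerance applies to both times, a 12-hour sample can fall anywhere from 0 to 24 hours after injury and so overlap the arrival window. This stands too.

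It can be said that parametric testing could include covariance analysis. The wording does not exclude it, but J.3 names models where it intends adjustment. If this analysis is intended, the section should say so before the data are seen.

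Finally, these are secondary or exploratory outcomes and the planned tests are valid. That is correct. It limits the importance of the point but does not remove it. Excluding late draws should not itself introduce bias: every patient receives both bags, and treating and research staff are blinded (H.3.2, H.5.2), so draw times should not depend on regimen.

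**Conclusion.** The point holds as a matter of efficiency only. J.3 leaves available arrival values out of the comparison of continuous 12- and 24-hour markers and 12-hour base deficit, and so gives up some precision. A reader might infer that the regimen comparison is biased or its intervals invalid. The documents do not support that, because the comparison is randomised and the unadjusted tests keep their error rate. Nor do they support a gain equal to nearly twice the patients: that needs rho near 0.7 and a pre-Bag B sample in every patient, and the documents establish neither.

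With at most about 166 per regimen, the variance reduction is 9% to 49% for rho 0.3 to 0.7 if f = 1, and 4.5% to 24.5% if f = 0.5. At rho 0.5 that is equivalent to about 221 or 190 patients per regimen. If the markers track weakly, the gain is negligible. It is an optional improvement to a secondary aim, with high confidence that the adjustment is not specified and medium confidence in the size of the benefit.

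**What to change.** In J.3, make analysis of covariance the main analysis of each continuous 12- and 24-hour marker and of 12-hour base deficit. Include regimen, site and the patient's own arrival value of the same measure, on the log or rank scale where the measure is skewed. Use the arrival value only when its recorded draw time precedes the start of Bag B. Otherwise treat it as missing, with the mean value and an indicator. State that the arrival value is not a baseline for prehospital tranexamic acid versus placebo, where it is measured after treatment.

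In the same amendment, reconcile the time origin (arrival in E.3.4, injury in I.3 and I.5) and say how samples in overlapping windows are assigned to a time point.

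No new blood samples are needed. The cost is SAP wording, some programming, and the availability of draw times and Bag B start times. Section N.3 does not list these among the in-hospital data elements, although they may be recorded elsewhere. If they cannot be recovered, the unadjusted comparison should remain the main analysis.
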